7.1.6 Subgroup analysis

Table 17 Subgroup analysis(MACE4 events)

Subgroup factor	A+T VS. A			T VS. A			A+T VS. T		
	HR(95%CI)		P	HR(95%CI)		P	HR(95%CI)		P
			Interaction P			Interaction P			Interaction P
Age									
<=65 years									
old									
>65 year old									
Sex									
Male									
Female									
Baseline ACS									
Yes									
No									
History of									
hypertension									
Yes									
No									
History of									
diabetes									
Yes									
No									
History of									
dyslipidemia									
Yes									
No									
History of									
smoking									
Yes									
No									
Baseline									
SYNTAX score									

<=22

23-32

>=33

Ditto for other

subgroups

表 18 Subgroup analysis(MACE5)

Note: The format is the same as Table 17.

表 19 Subgroup analysis(MACE3)

Note: The format is the same as Table 17.

表 20 Subgroup analysis(All-cause death)

Note: The format is the same as Table 17.

表 21 Subgroup analysis(Cardiovascular death)

Note: The format is the same as Table 17.

表 22 Subgroup analysis(Myocardial infarction)

Note: The format is the same as Table 17.

表 23 Subgroup analysis(Stroke)

Note: The format is the same as Table 17.

表 24 Subgroup analysis(Coronary revascularization)

Note: The format is the same as Table 17.

表 25 Subgroup analysis(Hospitalization for unstable angina)

Note: The format is the same as Table 17.

7.2 Exploratory Objectives

7.2.1 Baseline characteristics

Table 26 Demographic and baseline characteristics (grouped by total grafts failure at 1 year)

Indicator	Overall	Patency	Failure	P
Age				0.***
N(missing)	*** (***)	*** (***)	*** (***)	
mean(sd)	*** (***)	*** (***)	*** (***)	
median	***	***	***	
Min-Max	***~***	***~***	***~***	
p25-p75	***~***	***~***	***~***	
Sex				0.***
N(missing)	*** (***)	*** (***)	*** (***)	
Male	*** (***)	*** (***)	*** (***)	
Female	*** (***)	*** (***)	*** (***)	
Height				
N(missing)	*** (***)	*** (***)	*** (***)	
mean(sd)	*** (***)	*** (***)	*** (***)	
median	***	***	***	
Min-Max	***~***	***~***	***~***	
p25-p75	***~***	***~***	***~***	
Weight				0.***
N(missing)	*** (***)	*** (***)	*** (***)	
mean(sd)	*** (***)	*** (***)	*** (***)	

Indicator	Overall	Patency	Failure	P
median	***	***	***	
Min-Max	***~***	***~***	***~***	
p25-p75	***~***	***~***	***~***	
				0.***
BMI				0.***
N(missing)	*** (***)	*** (***)	*** (***)	
mean(sd)	*** (***)	*** (***)	*** (***)	
median	***	***	***	
Min-Max	***~***	***~***	***~***	
p25-p75	***~***	***~***	***~***	
				0.***
Clinical status				0.***
N(missing)	*** (***)	*** (***)	*** (***)	
Stable angina	*** (***)	*** (***)	*** (***)	
Unstable angina	*** (***)	*** (***)	*** (***)	
Non - ST-elevation myocardial infarction	*** (***)	*** (***)	*** (***)	
				0.***
History of myocardial infarction				0.***
N(missing)	*** (***)	*** (***)	*** (***)	
Yes	*** (***)	*** (***)	*** (***)	
No	*** (***)	*** (***)	*** (***)	
				0.***
Time since onset of myocardial infarction (day)				0.***
N(missing)	*** (***)	*** (***)	*** (***)	
<21	*** (***)	*** (***)	*** (***)	
21-90	*** (***)	*** (***)	*** (***)	

Indicator	Overall	Patency	Failure	P
>90	*** (***)	*** (***)	*** (***)	
CCS class				0.***
N(missing)	*** (***)	*** (***)	*** (***)	
0	*** (***)	*** (***)	*** (***)	
I	*** (***)	*** (***)	*** (***)	
II	*** (***)	*** (***)	*** (***)	
III	*** (***)	*** (***)	*** (***)	
IV	*** (***)	*** (***)	*** (***)	
NYHA class				0.***
N(missing)	*** (***)	*** (***)	*** (***)	
I	*** (***)	*** (***)	*** (***)	
II	*** (***)	*** (***)	*** (***)	
III	*** (***)	*** (***)	*** (***)	
IV	*** (***)	*** (***)	*** (***)	
History of hypertension				0.***
N(missing)	*** (***)	*** (***)	*** (***)	
Yes	*** (***)	*** (***)	*** (***)	
No	*** (***)	*** (***)	*** (***)	
History of hyperlipidemia				0.***
N(missing)	*** (***)	*** (***)	*** (***)	
Yes	*** (***)	*** (***)	*** (***)	
No	*** (***)	*** (***)	*** (***)	
History of smoking				0.***

Indicator	Overall	Patency	Failure	P
N(missing)	*** (***)	*** (***)	*** (***)	
Yes	*** (***)	*** (***)	*** (***)	
No	*** (***)	*** (***)	*** (***)	
History of diabetes				0.***
N(missing)	*** (***)	*** (***)	*** (***)	
Yes	*** (***)	*** (***)	*** (***)	
No	*** (***)	*** (***)	*** (***)	
History of peripheral vascular disease				0.***
N(missing)	*** (***)	*** (***)	*** (***)	
Yes	*** (***)	*** (***)	*** (***)	
No	*** (***)	*** (***)	*** (***)	
History of cerebrovascular accident				0.***
N(missing)	*** (***)	*** (***)	*** (***)	
Yes	*** (***)	*** (***)	*** (***)	
No	*** (***)	*** (***)	*** (***)	
History of peptic ulcer disease				0.***
N(missing)	*** (***)	*** (***)	*** (***)	
Yes	*** (***)	*** (***)	*** (***)	
No	*** (***)	*** (***)	*** (***)	
History of chronic kidney disease				0.***
N(missing)	*** (***)	*** (***)	*** (***)	

Indicator	Overall	Patency	Failure	P
Yes	*** (***)	*** (***)	*** (***)	
No	*** (***)	*** (***)	*** (***)	
LVEDD(mm)				
N(missing)	*** (***)	*** (***)	*** (***)	
mean(sd)	*** (***)	*** (***)	*** (***)	
median	***	***	***	
Min-Max	***~***	***~***	***~***	
p25-p75	***~***	***~***	***~***	
LVEF(%)				
N(missing)	*** (***)	*** (***)	*** (***)	
mean(sd)	*** (***)	*** (***)	*** (***)	
median	***	***	***	
Min-Max	***~***	***~***	***~***	
p25-p75	***~***	***~***	***~***	
LVEF class				
N(missing)	*** (***)	*** (***)	*** (***)	
30%-50%	*** (***)	*** (***)	*** (***)	
>50%	*** (***)	*** (***)	*** (***)	
SYNTAX score				
N(missing)	*** (***)	*** (***)	*** (***)	
Low(0-22)	*** (***)	*** (***)	*** (***)	
Intermediate(23-32)	*** (***)	*** (***)	*** (***)	
High(>=33)	*** (***)	*** (***)	*** (***)	
EuroScore score				

Indicator	Overall	Patency	Failure	P
N(missing)	*** (***)	*** (***)	*** (***)	
Low(0-2)	*** (***)	*** (***)	*** (***)	
Medium(3-5)	*** (***)	*** (***)	*** (***)	
High(>=6)	*** (***)	*** (***)	*** (***)	
Aspirin				0.***
N(missing)	*** (***)	*** (***)	*** (***)	
Use	*** (***)	*** (***)	*** (***)	
Not use	*** (***)	*** (***)	*** (***)	
beta_Blocker				0.***
N(missing)	*** (***)	*** (***)	*** (***)	
Use	*** (***)	*** (***)	*** (***)	
Not use	*** (***)	*** (***)	*** (***)	
ACEI or ARB				0.***
N(missing)	*** (***)	*** (***)	*** (***)	
Use	*** (***)	*** (***)	*** (***)	
Not use	*** (***)	*** (***)	*** (***)	
Statins				0.***
N(missing)	*** (***)	*** (***)	*** (***)	
Use	*** (***)	*** (***)	*** (***)	
Not use	*** (***)	*** (***)	*** (***)	
Proton pump inhibitor				0.***
N(missing)	*** (***)	*** (***)	*** (***)	
Use	*** (***)	*** (***)	*** (***)	

Indicator	Overall	Patency	Failure	P
Not use	*** (***)	*** (***)	*** (***)	
Cardiopulmonary bypass usage				0.***
N(missing)	*** (***)	*** (***)	*** (***)	
Yes	*** (***)	*** (***)	*** (***)	
No	*** (***)	*** (***)	*** (***)	

Table 27 Demographic and baseline characteristics (grouped by saphenous vein grafts failure at 1 year)

Note: Same as table 26, grouped only according to saphenous vein grafts failure at 1 year.

7.2.2 Major clinical events

Table 28 Occurrence of clinical events during the follow-up (grouped by total grafts failure at 1 year)

Indicator/Group	Overall occurrence of the event	Event rate 2-5 years during follow-up			
		24 months	36 months	48 months	60 months
MACE4					
Patency	*** (***)	**%	**%	**%	**%
Failure	*** (***)	**%	**%	**%	**%
MACE5					
Patency	*** (***)	**%	**%	**%	**%
Failure	*** (***)	**%	**%	**%	**%
MACE3					
Patency	*** (***)	**%	**%	**%	**%
Failure	*** (***)	**%	**%	**%	**%
All-cause death					
Patency	*** (***)	**%	**%	**%	**%
Failure	*** (***)	**%	**%	**%	**%
Cardiovascular death					
Patency	*** (***)	**%	**%	**%	**%
Failure	*** (***)	**%	**%	**%	**%

Event rate 2-5 years during follow-up

Indicator/Group	Overall occurrence of the event	24 months	36 months	48 months	60 months
Myocardial infarction					
Patency	*** (***)	**%	**%	**%	**%
Failure	*** (***)	**%	**%	**%	**%
Non-silent MI					
Patency	*** (***)	**%	**%	**%	**%
Failure	*** (***)	**%	**%	**%	**%
Stroke					
Patency	*** (***)	**%	**%	**%	**%
Failure	*** (***)	**%	**%	**%	**%
Coronary revascularization					
Patency	*** (***)	**%	**%	**%	**%
Failure	*** (***)	**%	**%	**%	**%

Table 29 Survival analysis for clinical events (grouped by total grafts failure at 1 year)

Indicator/Group	HR(95% CI)	Adjusted P
MACE4		
Failure VS. Patency	*** (***, ***)	0. ****
MACE5		
Failure VS. Patency	*** (***, ***)	0. ****
MACE3		
Failure VS. Patency	*** (***, ***)	0. ****
All-cause death		
Failure VS. Patency	*** (***, ***)	0. ****
Cardiovascular death		
Failure VS. Patency	*** (***, ***)	0. ****
Myocardial infarction		
Failure VS. Patency	*** (***, ***)	0. ****
Non-silent MI		
Failure VS. Patency	*** (***, ***)	0. ****
Stroke		
Failure VS. Patency	*** (***, ***)	0. ****
Coronary revascularization		
Failure VS. Patency	*** (***, ***)	0. ****

Table 30 Occurrence of clinical events (grouped by saphenous vein grafts failure at 1 year)

Note: same as table 28, grouped only according to saphenous vein grafts failure at 1 year.

Table 31 Survival analysis for clinical events (grouped by saphenous vein grafts failure at 1 year)

Note: same as table 29, grouped only according to saphenous vein grafts failure at 1 year.

Table 32 Grafts patency during 1-5 years follow-up

Indicator	Overall	Patency (A)	Failure (O/B)	Adjusted P
Total grafts at 1 year				0.***
N(missing)	*** (***)	*** (***)	*** (***)	
Patency (A)	*** (***)	*** (***)	*** (***)	
Failure (O/B)	*** (***)	*** (***)	*** (***)	
Saphenous vein grafts at 1 year				0.***
N(missing)	*** (***)	*** (***)	*** (***)	
Patency (A)	*** (***)	*** (***)	*** (***)	
Failure (O/B)	*** (***)	*** (***)	*** (***)	

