There are 500 patients were enrolled from July 2014 through November 2015 and follow-up was completed in January 2017, 168 patients in the T+A group, 166 in T group and 166 in A group. The results showed that the 1-year SVG patency rate (primary endpoint) of T+A group was 88.7% (432/487, T+A vs A, p=0.0006), the T group was 82.8% (371/485, T vs A, p=0.0962), and the A group was 76.5% (404/488). The incidence of MACE during 1 year of follow-up was 1.8% in T+A group, 2.4% in T group, and 5.4% in A group. The DACAB trial demonstrated that compared with aspirin monotherapy, the combination of ticagrelor and aspirin significantly improved 1-year SVG patency after CABG. Meanwhile, the combination of ticagrelor and aspirin therapy or ticagrelor monotherapy showed a favor trend with reducing the MACEs compared with aspirin monotherapy.

Would the observed differences in SVG patency at 1 year post CAGB translate into long-term clinical benefit? This remain to be a great interest to follow up these patients. Therefore, in present study, we intend to collect and analyze the long-term data in patients who were enrolled and survived in DACAB trial. We would observe the clinical outcomes of these subjects at 5-year post-CABG.

2. Study Objectives

- Primary Objective**

The primary objective is to compare the incidence of major adverse clinical events-4 (MACE-4, a composite of all-cause death, myocardial infarction, stroke, and coronary revascularization) among 3 randomized regimens in previous DACAB trial in the extended five-year follow-up after CABG.

- Secondary Objectives**

The secondary objectives are to compare the incidence of MACE-5 (a composite of all-cause death, myocardial infarction, stroke, coronary revascularization and hospitalization for unstable angina); MACE-3 (a composite of cardiovascular death, myocardial infarction and stroke); all-cause death; cardiovascular death; myocardial infarction; stroke; coronary revascularization; hospitalization for unstable angina and graft failure among 3 randomized regimens in previous DACAB trial in the five-year follow-up after CABG.

- Exploratory Objectives**

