4.3 Evaluation and Calculation of Endpoints

The primary outcome is the time to the first occurrence of any MACE-4, which is a composite of all-cause death, myocardial infarction, stroke, and coronary revascularization and measured in days since the date of randomization. Subjects who had not experienced any major adverse clinical events from randomization to the last visit will be right-censored. For those subjects who lost to follow-up at 5-year visit, the date of the last contact and the most updated clinical outcomes available in medical record or other source will be used in primary analysis. If there's no major adverse clinical events recorded for those subjects who lost to follow-up at 5-year visit, then these subjects will be right-censored at the date of their last contact. The survival curves will be estimated using Kaplan-Meier method.

The secondary outcomes (time to event) will be analyzed similarly with the primary observational endpoint.

Graft failure after CABG is in accordance with Fitzgibbon classification criteria by using MSCTA or CAG, there were a total of 3 categories, grade A, B and O, where grade A accounted for graft patency (no lesions), and grade B/O accounted for the graft failure.

5. Subject Selection Criteria

All the subjects enrolled in the DACAB trial.

6. Statistical Analysis

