6.2.4 Secondary Outcome

The time to event variables in the secondary outcomes will be analyzed similarly with the primary outcome.

As 1-4 vessels were generally measured in each subject, the vein graft patency at 5 years after CABG is a categorical data measured repeatedly in subjects. The number and the percentage of the grafts in Fitzgibbon grade B/O will be summarized by the group in previous DACAB study. GEE (Generalized Estimating Equations) was used to compare the subjects' saphenous vein graft patency rate among groups.

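### SAP Table 32 prints an adjusted P that mostly reflects grafts already failed at 1 year still being failed later, with no unit, test or at-risk set stated (exploratory, minor)

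*SAP*

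**What the plan says.** The last exploratory shell in SAP 7.2.2 is "Table 32 Grafts patency during 1-5 years follow-up". It has two blocks of rows, "Total grafts at 1 year" and "Saphenous vein grafts at 1 year", each split into patent (A) and failed (O/B). The columns give the later status on the same A versus O/B split, with an overall column and an adjusted P for each block.

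SAP 4.3 defines the grades once, with no separate rule for late reads: "where grade A accounted for graft patency (no lesions), and grade B/O accounted for the graft failure".

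No footnote removes the row already failed at 1 year, defines a new failure or names the units at risk. SAP 6.2 does not describe this table. Section 6.2.9 names a GLM for comparing outcomes between subject cohorts, and section 6.2.4 names GEE for comparing treatment groups. Table 13 says that grafts are its unit; Table 32 names no unit.

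Late imaging is not scheduled. Protocol 3.1 leaves it to clinical need, Protocol 5.2 takes patency from medical records, and Protocol 7.3 obtains original images where they exist.

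**The concern.** A graft graded B or O at 1 year sits in the failure column again at a later read unless it is re-graded A. The comparison of rows therefore mixes two things: failures that predate the window and have stayed failed, and new failures among grafts that were patent at 1 year. Only the second bears on whether 1-year status says anything about what happens afterwards.

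If persistence is high, the first component dominates and the P will be very small even when no graft fails after year 1. A reader who sees it could conclude that early failure predicts later failure. The neighbouring Table 28 uses the 1-year cohorts too, but its event-rate columns start at 24 months, so it looks forward from year 1. Table 32 has no equivalent restriction.

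**Working it through.** The plan gives no P, power or expected count for Table 32, so there is no figure to reproduce. The check asks what P the layout yields when later failure is unrelated to 1-year status.

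**Inputs from the documents (SAP 1, Background).** Patent vein grafts at 1 year: 432 + 371 + 404 = 1207. Grafts: 487 + 485 + 488 = 1460. Already failed: 1460 − 1207 = 253, or 253/1460 = 17.3%. The counts printed for T and A do not match their percentages (371/485 = 76.5%, printed as 82.8%; 404/488 = 82.8%, printed as 76.5%) and look interchanged. The pooled total is the same either way.

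**Clustering.** The SAP says "As 1-4 vessels were generally measured in each subject". On average 1460/500 = 2.92 vein grafts per subject, so with complete within-subject correlation the design effect is 1 + (2.92 − 1) × 1 = 2.92. A value of 2.2 is used as an intermediate assumption.

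**Assumed, because the documents give no figure.** Fraction re-imaged; new-failure rate among grafts patent at 1 year; persistence, meaning the share of 1-year failures still graded B/O later.

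**Formula.** With a, b = failed later and patent later among those failed at 1 year, and c, d = the same among those patent at 1 year:

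χ² = N(ad − bc)² / [(a+b)(c+d)(a+c)(b+d)], then divided by the design effect.

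**Central case.** Half re-imaged, full persistence, 10% new failure: a = 126, b = 0, c = 60, d = 544, N = 730.

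χ² = 730 × (126 × 544)² / (126 × 604 × 186 × 544) = 445. Divided by 2.2 this is 202, P about 6e-46.

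**Least extreme case in the grid** (re-imaged 30/50/80%, new failure 5/10/20%, persistence 100/90%, design effect 2.2). This is 30% re-imaged, 20% new failure, 90% persistence. Failed at 1 year: 0.3 × 253 = 75.9, of which 68.31 stay failed. Patent at 1 year: 0.3 × 1207 = 362.1, of which 72.42 fail. χ² = 141.0; 141.0/2.2 = 64.1; P about 1.2e-15.

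**Other graft-level settings, with design effect 2.92.**

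| Re-imaged | Persistence | New failure | χ² | χ²/2.92 | P |
|---|---|---|---|---|---|
| 100% | 100% | 0% | 1460 | 500 | about 1e-110 |
| 50% | 100% | 10% | 445 | 152 | about 5e-35 |
| 10% | 100% | 30% | 42.0 | 14.4 | 1.5e-4 |
| 5% | 100% | 50% | 10.8 | 3.7 | 0.055 |
| 25% | 90% | 70% | 10.7 | 3.7 | 0.055 |
| any | equal to new-failure rate | same | 0 | 0 | 1 |

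The first row shows the point most directly: nothing happens after year 1, and the P is still effectively zero.

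**Subject as unit (any failed graft).** Simulated with 600 runs per setting, 500 subjects, about 2.92 grafts each, full persistence, and new failures independent of 1-year status. With 50% re-imaged and 15% new failure per graft, the median P is about 1e-24 and every run rejects at 0.05. With 10% re-imaged and 50% new failure, the median P is 0.066 and 42% of runs reject.

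**Restricted comparison.** In the same simulation, the test used only grafts patent at 1 year and compared new failure by whether the subject had another failed graft at 1 year. It rejected in 3.0% to 6.7% of runs across 32 settings, close to the nominal 5%.

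**The case against.** Three stronger readings are tempting, and the documents do not support them.

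- *An extreme P is guaranteed whatever happens after year 1.* It is not. It needs B/O status to persist and enough grafts to be re-imaged. The SAP does not rule out a graft graded B being read as A later, and the re-imaged fraction is unknown because imaging follows clinical need. The table above includes settings with P = 0.055 and P = 1.
- *New failures are reported nowhere.* If the unit is the graft, the cell for patent at 1 year and failed later counts exactly these, and the overall cell of that row is the denominator. The table works as a transition table. What is missing is a test that addresses that cell.
- *The table follows the same grafts individually.* This is an inference. SAP 6.2.9 defines subject cohorts, and Table 32 names no unit. At subject level the problem remains but is weaker.

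It is also fair to say that the P is labelled as adjusted, whereas the check uses an unadjusted chi-square. The adjusting model is not named, so its P cannot be computed. With full persistence one cell is empty, and an ordinary logistic model would then have no finite estimate for 1-year status. The chi-square shows how strong the built-in association is; it does not predict the printed value.

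Finally, no stated objective asks whether 1-year failure predicts later failure. The exploratory objectives compare clinical events between the cohorts. That limits the consequence, but it also means that nothing in the plan depends on this P.

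**Conclusion.** The point holds in limited form. As laid out, Table 32 mixes persistence of 1-year failure with new failure, and its P mostly reflects persistence unless many failed grafts are re-graded A, few grafts are re-imaged, or new failure is very common. With 30-80% re-imaged, 5-20% new failure, at least 90% persistence and a design effect of 2.2, P is below 1e-14 with no true relation between 1-year status and later failure. These rates are assumptions; beyond them the P can be ordinary.

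Severity is minor. The table is exploratory, and neither the primary MACE-4 analysis nor the treatment-group patency comparison in Table 13 is affected.

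**What to change.** Keep the cross-tabulation as counts and row percentages, remove the P, and state whether the unit is the graft or the subject.

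If a test is wanted, restrict it to grafts graded A at 1 year that have a later read. Compare new failure (A to B/O) between subjects with and without another failed graft at 1 year, by GEE with the subject as cluster, and name the adjustment set.

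This changes one table shell and needs no new data. The restricted test uses fewer grafts: at most 1207 vein grafts, and fewer once those without a later read are dropped. It also asks a narrower question than the present layout. Because late imaging follows clinical need, subjects with a known failed graft may be re-imaged more often, and the simulated 3.0% to 6.7% does not cover that. The result should be labelled exploratory and shown with the number re-imaged in each group.

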7.3 Supplementary tables

Table 33 List of safety events

Table 34 List of concomitant medications
